## 4.2 Exclusion Criteria

1. Melanomas other than uveal melanoma (i.e. cutaneous, acral lentiginous, mucosal).
2. Metastatic uveal melanoma patients with bone-only disease.
3. Any other malignancy from which the patient has been disease-free for less than 2 years, with the exception of adequately treated and cured basal or squamous cell skin cancer, superficial bladder cancer or carcinoma in situ of the cervix, breast, or prostate.
4. Autoimmune disease: Patients with a history of inflammatory bowel disease, including ulcerative colitis and Crohn's Disease, are excluded from this study, as are patients with a history of symptomatic disease (e.g., rheumatoid arthritis, systemic progressive sclerosis [scleroderma], systemic lupus erythematosus, autoimmune vasculitis [e.g., Wegener's Granulomatosis]; motor neuropathy considered of autoimmune origin (e.g. Guillain-Barre Syndrome and Myasthenia Gravis).
5. Any underlying medical or psychiatric condition, which in the opinion of the investigator will make the administration of ipilimumab hazardous or obscure the interpretation of AEs, such as a condition associated with frequent diarrhea.
6. Any non-oncology vaccine therapy used for prevention of infectious diseases (for up to 1 month before or after any dose of ipilimumab).
7. Concomitant therapy with any of the following: tamoxifen, toremifene, IL-2, interferon, or other non-study immunotherapy regimens; cytotoxic chemotherapy; immunosuppressive agents; other investigation therapies; or chronic use of systemic corticosteroids greater than physiologic replacement doses. Ocular steroid use is acceptable.
  - a. Concomitant palliative radiation for the purposes of symptom management is allowed.
8. Women of childbearing potential (WOCBP), defined above in Section 4.1, who:
  - d. are unwilling or unable to use an acceptable method of contraception to avoid pregnancy for their entire study period and for up to 26 weeks after cessation of study drug, or
  - e. have a positive pregnancy test at baseline, or
  - f. are pregnant or breastfeeding.

9. Prisoners or subjects who are compulsorily detained (involuntarily incarcerated) for treatment of either a psychiatric or physical (e.g., infectious) illness.

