#### ***3.2.1.a Induction Phase***

During the induction phase, patients will be treated with nivolumab 1 mg/kg plus ipilimumab 3 mg/kg (+/- 7 days) for a total of four doses (week 1, 4, 7, 10). The induction phase continues through week 12.

During the induction phase, patients will also have a mandatory biopsy of tumor tissue for exploratory immune biomarker studies. This biopsy can occur any time after cycle 1 until the end of cycle 4 (weeks 4-12).

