## **5.3 Prohibited and Restricted Therapies During the Study**

### **5.3.1 Prohibited Therapies**

Patients in this study may not use vaccines for the treatment of cancer or prevention of disease unless indicated as a component of the protocol regimen (including those for common medical conditions) for up to one month pre and post dosing with ipilimumab. Concomitant systemic or local anti-cancer medications or treatments are prohibited in this study while receiving ipilimumab treatments.

Patients may not use any of the following therapies during the study:

- Any non-study anti-cancer agent (investigational or non-investigational)
- Any other investigational agents
- Any other (non-CA184024 related) CTLA-4 inhibitors or agonists
- Immunosuppressive agents
- Chronic systemic corticosteroids
- Any non-oncology vaccine therapies used for the prevention of infectious diseases (for up to 30 days prior to or after any dose of study drug).

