#### 6.4.2.a Definition of Measurable and Non-Measurable Lesions

- **Measurable Lesions** are lesions that can be accurately measured in two perpendicular diameters, with at least one diameter  $\geq 20$  mm and the other dimension  $\geq 10$  mm (10 mm x 10 mm for spiral CT). The area will be defined as the product of the largest diameter with its perpendicular. Skin lesions can be considered measurable.
- **Non-Measurable (evaluable) Lesions** are all other lesions, including unidimensionally measurable disease and small lesions (lesions without at least one diameter  $\geq 20$  mm), and any of the following:
  - Lesions occurring in a previously irradiated area (unless they are documented as new lesions since the completion of radiation therapy), bone lesions, leptomeningeal disease, ascites, pleural or pericardial effusion, lymphangitis cutis/pulmonis, abdominal masses that are not pathologically/cytologically confirmed and followed by imaging techniques and cystic lesions.
  - All measurable and non-measurable lesions should be measured at screening and at the defined tumor assessment timepoints (see Section 5, Table 2). Extra assessments may be performed, as clinically indicated, if there is a suspicion of progression.

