#### 6.4.2.b Definition of Index/Non-Index Lesions

All measurable lesions, up to a maximum of **five lesions per organ** and **ten lesions in total**, should be identified as *index* lesions to be measured and recorded on the medical record at Screening. The *index* lesions should be representative of all involved organs. In addition, *index* lesions should be selected based on their size (lesions with the longest diameters), their suitability for accurate repeat assessment by imaging techniques, and how

representative they are of the patient's tumor burden. At Screening, a sum of the products of diameters (SPD) for all *index* lesions will be calculated and considered the baseline sum of the products of diameters. Response criteria to be followed are listed below. The baseline sum will be used as the reference point to determine the objective tumor response of the *index* lesions at tumor assessment (TA).

Measurable lesions, other than *index* lesions, and all sites of non-measurable disease, will be identified as *non-index* lesions. *Non-index* lesions will be recorded on the medical record and should be evaluated at the same assessment time points as the *index* lesions. In subsequent assessments, *non-index* lesions will be recorded as "stable or decreased disease," "absent," or "progression."

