**6.4.3.e Immune-Related Best Overall Response Using irRC (irBOR)**

irBOR is the best confirmed irRC overall response over the study as a whole, recorded between the date of first dose until the last tumor assessment before subsequent therapy (except for local palliative radiotherapy for painful bone lesions) for the individual subject in the study. For the assessment of irBOR, all available assessments per subject are considered.

irCR or irPR determinations included in the irBOR assessment must be confirmed by a second (confirmatory) evaluation meeting the criteria for response and performed no less than 4 weeks after the criteria for response are first met.

For metastatic patients, imaging of the chest, abdomen and pelvis is required at screening (ie, baseline) and at each tumor assessment visit, regardless of the location of known metastases. Refer to Section 6.1 Time and Events Schedule for further information. Similar methods of tumor assessment and similar techniques must be used to characterize each identified and reported lesion at screening and during subsequent tumor assessments. Imaging-based evaluation is preferred to clinical examination. For adjuvant patients, imaging of the chest, abdomen and pelvis is required at baseline and at Week 24 (+/- 7 days) and every 6 months thereafter (+/- 7 days) until removal from or completion of study.

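### Palliative radiation is allowed in 4.2 but conflicts with 5.3.1 during the ipilimumab period, and no rule says how an index lesion irradiated on study counts toward response

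*Combined protocol and SAP*

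**What the plan says.** **On whether radiation may be given.** Section 4.2 item 7a: "Concomitant palliative radiation for the purposes of symptom management is allowed". It sets no limit on anatomical site, on index lesions or on treatment phase. The document history lists this permission as the only change in this version besides the cover page. Exclusion 7 in the synopsis does not carry it. Section 5.3.1 says: "Concomitant systemic or local anti-cancer medications or treatments are prohibited in this study while receiving ipilimumab treatments". That sentence does not name radiation and has no palliative exception. The list in 5.3.1 for the whole study bars "Any non-study anti-cancer agent (investigational or non-investigational"), which also does not name radiation. Ipilimumab is given in induction only, "for a total of four doses (week 1, 4, 7, 10). The induction phase continues through week 12" (Section 3.2.1.a).

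**On how irradiated lesions are assessed.** Section 6.4.2.a lists among non-measurable lesions "Lesions occurring in a previously irradiated area (unless they are documented as new lesions since the completion of radiation therapy), bone lesions" and others. Section 6.4.2.b selects index lesions at screening and adds: "The baseline sum will be used as the reference point to determine the objective tumor response of the" index lesions. Section 6.4.3.e counts assessments for immune-related best overall response (irBOR) up to the last one "before subsequent therapy (except for local palliative radiotherapy for painful bone lesions"). Section 9 and the synopsis define response as RECIST CR + PR and attach no radiation rule. Section 9 rejects a 5% response rate if at least 4 of 27 patients respond, with stated errors of 4.4% (type I) and 18.2% (type II).

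**The concern.** There are two linked problems.

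The first is a contradiction over permitted treatment. During induction, the investigator and the monitor cannot tell from the text whether palliative radiation is allowed or is a protocol deviation.

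The second concerns the primary endpoint. Radiation can shrink the lesion it is aimed at. If that lesion belongs to the baseline sum and stays in the follow-up sum, its shrinkage is credited to nivolumab plus ipilimumab. Section 4.1 requires only one measurable lesion for entry, so the irradiated lesion can be the whole sum. Efficacy is judged by the investigator or a designee (Section 6.4.2), and Table 10 has no entry for radiation. With a cut-off of 4 responders, one misattributed response can decide the trial. Settling the handling after responses are known would also be open to bias.

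**Working it through.** **Step 1: the passages on permission.**

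| Period | 4.2 item 7a | 5.3.1 | Result |
|---|---|---|---|
| Ipilimumab period (doses at weeks 1, 4, 7, 10) | palliative radiation allowed | local anti-cancer treatment barred, no exception | conflict |
| Nivolumab maintenance | palliative radiation allowed | only the whole-study list applies, and it refers to agents | no conflict shown |

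**Step 2: which response rules reach an index lesion irradiated on study.**

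- 6.4.2.a speaks of areas already irradiated. It does not expressly reclassify an index lesion irradiated after screening, and 6.4.2.b keeps the screening sum as the reference.
- 6.4.3.e exempts only radiotherapy for painful bone lesions from the cut at subsequent therapy. That suggests other radiotherapy closes the irBOR window. It does not say whether permitted concomitant radiation is subsequent therapy.
- Bone lesions are non-measurable under 6.4.2.a and so cannot be index lesions. The exempted radiotherapy cannot shrink the index sum.
- Section 9 (RECIST CR + PR) has no cut and no lesion rule.

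**Step 3: who is exposed.** Under the immune-related criteria, partial response needs a 50% fall in the sum of products. Let the irradiated lesion hold a share s of the baseline sum and shrink by a fraction f, with the other lesions unchanged. The fall is s × f. Since f is at most 1, local shrinkage alone gives a partial response only if s is at least 0.5. The risk is therefore concentrated in patients with one or few index lesions.

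**Step 4: reproduce the design.** Inputs from Section 9: n = 27, cut-off 4, null 5%, alternative 20%. Let X be the number of responders.

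- Type I error: P(X ≥ 4 | 27, 0.05) = 0.0437, the stated 4.4%.
- Type II error: P(X ≤ 3 | 27, 0.20) = 0.1823, the stated 18.2%.
- P(X = 3 | 27, 0.05) = 0.107: under the null, the trial ends one responder short about one time in nine.

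**Step 5: illustrations at a true rate of 5%.** The documents give no frequency of on-study radiation or of responses produced by it. Every rate below is an assumption.

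(a) One of the 27 is certain to be a false responder, so the other 26 need 3: P(X ≥ 3 | 26, 0.05) = 0.139.

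(b) Each true non-responder has probability q of being misclassified, so p = 0.05 + 0.95q.

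(c) Only 4 patients are exposed. X is then the sum of a binomial (23, 0.05) and a binomial (4, p). The 4 is 27 − 23, because Section 9 records 23 evaluable patients at the 2017 design change. It assumes that the radiation permission came no earlier than that change and that nobody already enrolled was still at risk.

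| q | p | (b) all 27 exposed | (c) 4 exposed |
|---|---|---|---|
| 1% | 0.0595 | 7.4% | 4.8% |
| 2% | 0.0690 | 11.2% | 5.2% |
| 3% | 0.0785 | 15.8% | 5.6% |

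**The case against.** The strongest reply is that the existing text already does most of the work. Item 7a is the specific and most recent wording, so it can be read as governing the general sentence in 5.3.1. The bone exception in 6.4.3.e has a purpose only if other radiotherapy ends the irBOR window, so later scans would not count. Section 6.4.2.a is a lesion definition and could be applied at every assessment. Immune-related responses need confirmation at least 4 weeks later, and index lesions should represent all involved organs, so one irradiated lesion will often be too small a share to matter. Section 9.1 invokes RECIST 1.1 without reproducing it, and whether that standard supplies a rule cannot be judged from these documents.

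Much of this stands, and it limits the point. It does not close the gap. The helpful readings are inferences: none is stated, and the irBOR cut is not carried into the endpoint of Section 9. Confirmation does not help where shrinkage after radiation lasts.

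A reader might infer three stronger things that the documents do not support:

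- *That radiation is prohibited throughout the study.* Section 5.3.1 does not name radiation, and its bar on local treatment runs only while ipilimumab is given.
- *That the protocol is silent on radiation in response assessment.* Sections 6.4.2.a and 6.4.3.e both address it, incompletely.
- *That the design's type I error is 13.9%.* That figure is conditional on a false responder being present. The design's own figure is 4.4%, and it reproduces.

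**Conclusion.** The point holds in limited form and should be fixed. Item 7a of 4.2 and 5.3.1 conflict for the ipilimumab period, and the synopsis is out of step with 4.2. In both treatment phases, no stated rule keeps shrinkage of an index lesion irradiated on study out of the primary endpoint. Patients with one or few index lesions are the ones mainly affected.

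The actual bias cannot be computed from the documents. The figures show only how sensitive a 4-of-27 rule is. Misclassification of 1% to 3% of non-responders takes 4.4% to between 7.4% and 15.8% if all 27 patients are exposed, and to between 4.8% and 5.6% if only 4 are. The low end is a small effect, so the case for acting rests on the ambiguity and the low cost of removing it, not on a demonstrated error rate.

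**What to change.** 1. Reconcile 4.2 item 7a, 5.3.1 and exclusion 7 of the synopsis. Whether and when palliative radiation is permitted is for the sponsor to decide.

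2. In 6.4 and Section 9, state one endpoint rule, the same for every response criterion used:
   - An index or target lesion irradiated on study is not evaluable for response from that date.
   - A response counts only if it was met before the radiation, or is met on non-irradiated lesions with the irradiated lesion removed from **both** the baseline and the follow-up sums. Removing it from follow-up alone would itself create apparent shrinkage.
   - A patient with no remaining index lesion and no earlier response is a non-responder and stays in the denominator.

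3. Align the bone-radiotherapy exception in 6.4.3.e with this rule, and record the site and date of any on-study radiation.

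The cost is a few lines of text and one case report form item. The downside is that a few irradiated patients may not be classifiable as responders. If one of the 27 could not count, power at a 20% response rate would be P(X ≥ 4 | 26, 0.20) = 79.3%, against 81.8% (1 − 0.182) as planned. The rule governs measurement only and does not restrict treatment.

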### **4.3 Data Safety Monitoring Plan**

MD Anderson Cancer Center (MDACC) will monitor the progress of all clinical investigations being conducted under its IND and remain compliant under 21CFR312.56(b). The clinical research monitor, who has not had a prior role in the conduct of the study, will be assigned to monitor the study and will discuss the frequency of the chart review with the PI and the study manager. For all studies, eligibility and informed consent documentation will be reviewed following enrollment of selected subjects. With the exception of eligibility and informed consent review, the PI and the study manager will receive notification from the clinical research monitor approximately 2 weeks prior to each monitoring visit. The study coordinator or research nurse will be responsible for providing the monitor with any additional supporting documents and regulatory binders.

The frequency of the monitoring visits will occur every 8-12 weeks or more or less frequently as determined by the activity of the clinical trial.

Source documentation will be reviewed and used to independently verify study data. Data quality will be assessed by measuring it against the standards for optimal data as delineated in the research protocol. Investigator compliance with regulatory requirements and guidelines for Good Clinical Practice (GCP) will be assessed.

The clinical research monitor will complete a written monitoring report following each monitoring visit. The report will include a summary of what the monitor reviewed, any significant findings, identified actions taken or to be taken by the research team, and/or actions recommended securing compliance. Emphasis will be placed on clear and complete reporting of the findings. Comments will be made regarding problems or concerns affecting the validity or accuracy of the data.

The final report will be submitted to the MDACC IND Medical Monitor for review. The original signed report will be kept in the IND folder within the IND Office. A follow-up letter identifying unresolved issues will be sent to the PI to be kept in the regulatory binder. In order to remain compliant with 21CFR312.56(b) any trial that is being conducted under an MDACC-sponsored IND and is discontinued due to investigator noncompliance will have official notification set to the FDA.

## 5 STUDY THERAPY

### 5.1 Nivolumab (BMS 936558)

Nivolumab (BMS-936558) vials must be stored at a temperature of 2°C for review. The vials must be protected from light and freezing. If stored in a glass front refrigerator, vials should be stored in the carton. Recommended safety measures for preparation and handling of nivolumab include laboratory coats and gloves.

#### Nivolumab Injection, 100 mg/10 mL (10 mg/mL) and 40 mg/4 mL (10 mg/mL)

Vials of nivolumab injection must be stored at 2°-8°C (36°-46°F) and protected from light, freezing, and shaking.

#### Undiluted Nivolumab Injection and Diluted Nivolumab Injection in the IV Bag

The administration of nivolumab infusion must be completed within 24 hours of preparation. If not used immediately, the infusion solution may be stored under refrigeration conditions (2°-8°C, 36°-46°F) for up to 24 hours, and a maximum of 4 hours of the total 24 hours can be at room temperature (20°-25°C, 68°-77°F) and room light. The maximum 4-hour period under room temperature and room light conditions includes the product administration period.

Care must be taken to assure sterility of the prepared solution as the product does not contain any anti-microbial preservative or bacteriostatic agent. No incompatibilities between nivolumab and polyolefin bags have been observed. Nivolumab is to be administered before ipilimumab as a 60-minute IV infusion, using a volumetric pump with a 0.2/0.22 micron in-line filter at the protocol-specified dose. The drug can be diluted with 0.9% normal saline for delivery but the total drug concentration of the solution cannot be below 0.35 mg/ml. It is not to be administered as an IV push or bolus.

When the combination of nivolumab and ipilimumab are to be administered on the same day, separate infusion bags and filters must be used for each infusion. Nivolumab is to be administered first. The second infusion will always be ipilimumab and will start no sooner than 30 minutes after completion of the nivolumab infusion. Ipilimumab may be diluted in 0.9% Sodium Chloride Solution or 5% Dextrose solution. Nivolumab may be diluted in 0.9% Sodium Chloride Solution.

The dosing calculations should be based on body weight. If the subject's weight on the day of dosing differs by > 10% from the weight used to calculate the dose, the dose must be recalculated. All doses should be rounded up to the nearest milligram per institutional standard. There will be no dose modifications allowed.

### 5.2 Ipilimumab

Ipilimumab injection can be used for IV administration without dilution after transferring

to a PVC (polyvinyl chloride), non-PVC/non-DEHP (di-(2-ethylhexyl)phthalate) or glass containers and is stable for 24 hours at 2-8°C without dilution after transferring storage instructions, refer to ipilimumab IB and/or pharmacy reference sheets.

Recommended safety measures for preparation and handling include protective clothing, gloves, and safety cabinets.

Ipilimumab is to be administered as a 90-minute IV infusion, using a volumetric pump with a 0.2 to 1.2 micron in-line filter at the protocol-specified dose. The drug can be diluted with 0.9% normal saline or 5% Dextrose Injection to concentrations between 1 mg/mL and 4 mg/mL. It is not to be administered as an IV push or bolus injection. Care must be taken to assure sterility of the prepared solutions, since the drug product does not contain any antimicrobial preservatives or bacteriostatic agents. At the end of the infusion, flush the line with a sufficient quantity of normal saline or 5% dextrose solution.

When both study drugs are to be administered on the same day, separate infusion bags and filters must be used for each infusion. Nivolumab is to be administered first. The nivolumab infusion must be promptly followed by a saline flush to clear the line of nivolumab before starting the ipilimumab infusion.

Ipilimumab infusion will start no sooner than 30 minutes after completion of the nivolumab infusion. During **the induction phase**, subjects may be dosed no less than 19 days between doses. If dosing is delayed, both nivolumab and ipilimumab must be delayed together. If dosing is resumed after a delay, both nivolumab and ipilimumab must be resumed on the same day.

During the **maintenance phase**, subjects may be dosed no less than 24 days between doses. Subjects may be dosed up to 3 days after the scheduled date if necessary. Subsequent dosing should be based on the actual date of administration of the previous dose of drug. Ipilimumab may be diluted in 0.9% Sodium Chloride Solution or 5% Dextrose solution. Nivolumab may be diluted in 0.9% Sodium Chloride Solution.

